3.4 Withdrawals

Patients can withdraw from the study whenever they wish, and do not have to give a reason, although any reasons given must be documented. Their subsequent treatment will not be affected in any way. Patients may also withdraw from the questionnaire element of the study but be retained for other follow up. Any patients lost must be traced and documented whenever possible.

Wherever possible, data missing because of withdrawal will be imputed from available data.

Section 4: LINKS BETWEEN OBJECTIVES & OUTCOMES

4.1 Trial Objective 1 'Compare costs, processes and outcomes of care between experimental and control groups'

Objective 1a Patient Outcomes

- | | | |
|---|---|--------------------------|
| 1 | Number of further reported contacts or deaths | [primary outcome] |
| 2 | Time to the first reported contact or death | [primary outcome] |

Primary outcomes will be analysed using the hierarchy of outcomes (comprising 999 calls, ED attendances, emergency admissions, and death) established in SAFER1^[4].

- 3 Injuries related to further falls **[secondary outcome]**
This will be summarised by cross-tabulation of the numbers and proportions in each study group, split by types of injuries.
- 4 Health-related Quality of Life **[secondary outcome]**
This is measured by SF-12 and derived SF-6D, and will be assessed and summarised at one month and six months.
- 5 Satisfaction **[secondary outcome]**
This is measured by the Quality of Care Monitor, and will be assessed and summarised at one month.
- 6 Psychological status **[secondary outcome]**
This is measured by the mFES, and will be assessed and summarised at one month and six months.
- 7 Change in place of residence at six months **[secondary outcome]**

Objective 1b Processes of Care

- 1 Pathway of care **[secondary outcome]**
This is measured by health and social care contacts associated with the index fall and during follow-up period, split by types of contacts and adjusted by covariates.
- 2 Ambulance service operational indicators **[secondary outcomes]**
These comprise episode of care and job cycle times, adjusted by covariates.
- 3 Protocol compliance **[secondary outcome]**
This will be measured by a series of data items related to protocol compliance (such as the completion of clinical documentation; referral processes).

Objective 1c Cost of Care **[secondary outcome]**

This objective is addressed by estimating and comparing the resources utilised in both groups, adopting a 'bottom-up approach' from the perspective of the NHS, personal social services, and patients and their families. Specifically:

- 1 Estimation of costs of providing the intervention
Data relating to direct costs to the NHS will be assessed using data logged as a part of routine practice and from resource utilisation recording sheets, together with reference to patient records and discussions with relevant finance staff. Resources used will be translated into costs using relevant published unit costs.
The number of non-conveyances will be logged, and potential impact on costs to the ambulance service and hospital emergency departments estimated.
Further, the additional costs to community services will be documented and costs using relevant published unit costs.
- 2 Costs to patients and families
Patients and their families will complete a self-administered questionnaire specifically designed for this study but based on other instruments catalogued within the Database of Instruments for Resource Use Management (www.dirum.org).

Further, data on the use of the health service and social services resources will be collected for each patient using a combination of paramedic records and routine hospital records (for hospital events). Data relating to social services costs will be derived from discussion with relevant social services departments

4.2 Trial Objective 2 ‘Estimate wider system effects of the introduction of the intervention on ambulance service performance and costs’

We consider this objective two parts.

Objective 2a Wider effect on operational indicators

Ambulance service operational indicators **[secondary outcomes]**

Response times across the study catchment and surrounding areas during the trial period will be compared to pre-trial response times and ‘rest of service’ response times (adjusted for pre-trial differences) in order to identify any knock on or halo effects.

Objective 2b Wider effect on Costs of Care [secondary outcome]

Consequences of the scheme for the wider NHS and social services (eg ED attendances, inpatient admissions, GP consultations, out-of-hours GP contacts, NHS Direct contacts, social services utilisation) will be estimated using a combination of routine data sources, discussions with staff from relevant departments (eg social services) and from responses to patient completed questionnaires that highlight service contacts and utilisation..

Further, the time spent by ambulance staff with patients and the nature of their involvement will be documented so as to determine the direct cost of patient care, cost of patient transportation and other costs – reflecting travel, time spent at ED discharging patients and so on.

4.3 Trial Objective 3 ‘Gain an in-depth understanding of how the intervention is experienced by patients’

This objective is addressed using face-to-face semi-structured interviews conducted in co-operation with a carer or older person present at time of fall. Qualitative interviews to be undertaken with patients who: experienced a fall; were recruited to the trial; seen by an intervention paramedic and agreed to the interview. This will include patients: who were taken to ED; referred to a falls service; and patients who were neither taken to the ED nor referred to a falls service.

The aims of the interviews are to explore:

- Patient experience of ambulance service
- Patient experience of those seen by a falls service
- Patient health since fall
- Patient satisfaction with treatment

4.4 Trial Objective 4 ‘Understand how the intervention is delivered in practice, identifying factors which enable or hinder its use’

This objective is addressed using focus groups carried out with intervention paramedics ‘pre’ and ‘post’ trial. Focus groups will be carried out by two researchers, one to lead discussions and one to take notes and enable the linkage of texts to speakers as well as concerning other details, such as points of consensus or disagreement, issues that drew strong emotional responses such as anger, fear or anxiety.

The aims of the focus groups are to explore:

- Paramedics views and attitudes toward the new intervention
- Any preconceptions about the new way of working

- Factors which enable the use of the new referral pathway
- Factors which hinder the use of the new referral pathway

4.5 Trial Objective 5 'Inform the development of methods for falls research in relation to outcomes assessment'

We shall compare mFES scores with SF-12 component scores and derived SF-6D scores as recommended by Prevention of Falls Network Europe (ProFaNE)^[9] group to establish construct validity. We shall assess predictive validity by comparing mFES scores with the mean number of further falls and time to first subsequent fall.

Section 5: MAIN ANALYSES

5.1 Statistical Analysis

This will conform to principles outlined in WWORTH SOP28 Statistics^[5]; specifically, the primary analysis will be by 'treatment allocated', reflecting the pragmatic nature of the trial design where patients are cared for by paramedics based at ambulance stations randomly allocated to deliver intervention or control care.

Primary outcomes comprise a hierarchy relating to further emergency healthcare contacts for falls, as measured by contacts with the 999 service, Emergency Department (ED) or emergency admission to hospital for a further fall, or deaths within six months of the index fall. Important predictors that may affect triage decisions and outcomes, including the distance between incidents and EDs at index fall, patient age and gender, patterns of presentation (eg, whether out-of-hours or not) will be considered as covariates, and included in statistical modelling. We shall also take account of potential confounders such as the sequence of base stations (and their trial allocation) from which paramedics attend patients who fall more than once. The principles used in analysing primary outcomes also apply to quantitative secondary outcomes.

Required analyses include: logistic regression (for binary outcomes); cross-tabulations and risk ratios (for categorical outcomes); and survival analysis, including Cox's proportional hazards models^[10], (for measurement outcomes, such as times to events). Primary outcomes will also be jointly analysed using methods developed for recurrent event analysis^[11-14]. Repeated observations will be analysed in two ways: as 'repeated measures'; and summarised by "area under curve" of HRQoL measures per patient.

Where appropriate, multilevel modelling will be used to estimate clustering effects for stations or centres. The exact number of levels in models will be determined using statistically significant changes in likelihood ratio tests according to the principle of parsimonious parameterisation. Potential covariates to be included in models will be tested; those with an F value of less than 1 (that is, they increase the standard error of the estimate) will be excluded and the analysis recalculated. Binary covariates where almost all cases (>90%) are in one category will also be excluded.

Residual diagnostics will be used where analyses assume Normality; if the distributions of residuals are markedly non-normal, data transformation or bootstrapping will be considered. Residual analysis will be used to identify outliers; identified outliers will be excluded and the analysis updated. Wherever possible, outcome descriptions, summaries and comparisons will be expressed in accordance with appropriate CONSORT (www.consort-statement.org) guidelines, including estimates with 95% confidence intervals (allowing two-tailed tests at the 5% significance level).

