3.1 Data Sources & Collection

Our primary outcome is “further emergency healthcare contacts (999 call or Emergency Department (ED) attendance or hospital admission) or death for any reason and for falls per recruited faller, and time to first contact or death” for six months following the index call. This CRT does not approach participants at the point of treatment, because they may be in distress and unable to give informed consent, but seeks instead retrospective consent to follow up through routine medical records and by postal questionnaire. We planned to follow-up all our patients anonymously in order to achieve the primary outcome for our target sample size. In Wales, arrangements for this process are already in place through the existing SAIL (Secure Anonymised Information Linkage) Database, and our application for permission through the Information Governance Review Panel has been granted. We applied to the NIGB Ethics and Confidentiality Committee for permission to follow-up our patients anonymously through the Information Centre in England and permission has been granted for this process. Conditional to this permission, people who have clearly dissented to identifiable follow-up must be excluded from the study. For clarity, if a patient has at any time declined to be part of the study (either in returning a consent form or orally on the telephone) they will be removed from the study.

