3.2 Sample Size and Statistical Power

We made the conservative estimate that trial patients have about 50% chance of making another emergency contact within six months; in the absence of intra-cluster correlation (ICC), a sample of 4190 evaluable participants yields 90% power, when using two-sided 5% significance level, of detecting a change in this chance from 50% to <45% or to >55%. The analogous outcome in the SAFER 1^[4] trial indicated an ICC of zero in clusters of participants seen by paramedics from the same ambulance station. To be conservative, we therefore allowed for an ICC of 0.002, and sought 251.6 (calculated from $0.998 \cdot 4190 / (25 - 0.002 \cdot 4190)$) participants per ambulance station, making a total sample size target of 6290.

However, actual recruitment is slightly lower, at 5939 participants, and we will lose approximately 1000 patients that decline to be part of the study. Furthermore, previous experience suggests that we shall also lose about 10% of the remaining patients from analysis because we shall not be able to match them with their routine electronic data on contacts with the NHS. Hence we expect the recruited sample of 5939 participants to yield only 4400 suitable for accurate information linkage. With an ICC of 0.002 and equal cluster sizes, this expected evaluable sample size corresponds to 3260 independent participants, which, in turn, equates to approximately 80% statistical power. In short, the cumulative loss in recruitment, and from dissenting and un-matched patients will reduce the statistical power of SAFER 2 from a conservative 90% to the traditional 80%, even allowing for more intra-cluster correlation than observed in the SAFER 1^[4] trial.

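### The primary outcome covers any-reason and falls contacts in one section and falls contacts only in another, with two labelled primaries, no single decisive test, and power stated for only part of the set

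*SAP*

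**What the plan says.** - **Section 3.1** gives a primary outcome, in the singular, that already holds two causes and two forms: contacts "or death for any reason and for falls per recruited faller, and time to first contact or death", over six months from the index call. Objective 1a in section 2 also names both causes.
- **Section 4.1** labels two outcomes as primary without stating cause: "Number of further reported contacts or deaths" and "Time to the first reported contact or death". It adds: "Primary outcomes will be analysed using the hierarchy of outcomes", with four components (999 calls, ED attendances, emergency admissions, death) taken from SAFER 1.
- **Section 5.1** restricts the contacts: "Primary outcomes comprise a hierarchy relating to further emergency healthcare contacts for falls". The list ends with "emergency admission to hospital for a further fall, or deaths within six months of the index fall", so the contacts are limited to falls but the deaths carry no cause restriction. It then lists logistic regression, Cox models and a joint recurrent-event analysis, and names none as decisive. Its closing paragraph sets 95% intervals and two-tailed 5% tests as the general level.
- **Section 3.2** powers a binary quantity: "trial patients have about 50% chance of making another emergency contact within six months". It mentions neither falls nor death.
- **Section 1** says that the binary sample size also suffices for time to first event. It says nothing about counts.

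**The concern.** A 999 call for chest pain counts under the any-reason reading of section 3.1 and does not count under section 5.1. Section 4.1 cannot settle the matter because it is silent on cause. The choice between number and time is also open, as is the choice among the models in section 5.1.

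Two things are at stake. First, the primary result is not determined by the plan, so the choice could be made, or could appear to have been made, after the data are seen. If several versions are each read at 5%, the chance of at least one false positive exceeds 5%. Second, a reader will attach the stated 80% power to whatever is reported as primary, although it was derived for one version only.

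**Working it through.** **1. Reproduce the SAP's own figures (section 3.2).** Inputs: 50% v 45%, two-sided 5%, 90% power, ICC 0.002, 25 stations.

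- Per arm, pooled-variance formula: n = [1.960·√(2·0.475·0.525) + 1.2816·√(0.5·0.5 + 0.45·0.55)]² / 0.05² = 2094.2, rounded up to 2095. Two arms: 4190, as stated.
- Cluster size: 0.998·4190 / (25 − 0.002·4190) = 251.6. Times 25 = 6290, as stated.
- Effective size from 4400 evaluable: mean cluster 4400/25 = 176; design effect 1 + 175·0.002 = 1.35; 4400/1.35 = 3259 (stated 3260).
- Power with 1630 per arm, 50% v 45%: 81.6% (stated as about 80%).

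The sample-size arithmetic is sound.

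**2. Does it extend to time to first event, as section 1 says?** Assume proportional hazards and take 50% and 45% as the six-month risks.

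- HR = ln(0.55)/ln(0.50) = 0.862.
- Events = 3260·(0.50 + 0.45)/2 = 1548.5.
- Power = Φ(|ln 0.862|·√1548.5/2 − 1.960) = Φ(2.910 − 1.960) = 82.9%.

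The statement in section 1 is supported for any-cause events.

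**3. Does it extend to a falls-only outcome?** The SAP gives no falls-only risk, so the risks below are assumptions, and they leave out the deaths that section 5.1 includes. The effect is section 1's criterion of one event in ten, taken as a 10% relative reduction, with 1630 effective participants per arm and the pooled-variance test used in step 1.

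| Control risk | Comparison | Power |
|---|---|---|
| 50% | 50% v 45% | 81.6% |
| 30% | 30% v 27% | 47.5% |
| 20% | 20% v 18% | 30.7% |

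No power statement is given for the count either, and none can be derived, because the SAP gives no event rate or dispersion.

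**4. Family-wise error if each version is tested at two-sided 5%.** The versions share events, so their test statistics must be positively correlated. The correlations are assumptions; results come from simulating equicorrelated normal statistics under the null.

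| Tests | r = 0.7 | r = 0.8 | r = 0.9 |
|---|---|---|---|
| 2 (number, time) | 8.3% | 7.8% | 7.0% |
| 4 (two causes by two forms) | 13.0% | 11.4% | 9.4% |

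**5. Power if several primaries are kept.** With a Bonferroni split and 3260 effective participants, power for 50% v 45% is 73.2% with two tests (alpha 0.025) and 64.1% with four (alpha 0.0125). For 80% power these would need 3790 and 4448 effective participants. One named test at 5% keeps 81.6%.

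**The case against.** Several points on the other side stand.

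- Section 3.1 is not an all-cause definition that section 5.1 contradicts outright. It names both causes, so the conflict is both versions against falls contacts only. Section 5.1 is not wholly falls-only either, because its deaths are not restricted by cause.
- A reader might infer that neither listed primary is powered. Section 1 answers this for time to first event, and step 2 confirms it. Logistic regression for binary outcomes is also in section 5.1.
- A reader might quote a family-wise error of 18% for four tests (1 − 0.95⁴ = 18.5%). That needs independence, which is impossible when falls contacts are nested within all contacts and number and time use the same events.
- The SAP states no rule for declaring success, and the 5% level comes from a general reporting sentence. That the sponsor would claim whichever version is significant is therefore not something the document says. The SAFER 1 hierarchy and the statistics SOP that section 5.1 follows are not at hand, and might set an order. As written in the SAP, the hierarchy lists event types and is not a testing sequence.
- The low falls-only power depends on holding the effect at one in ten. A 5-point absolute reduction would have 89% power from 30% and 96% from 20%. Those are reductions of one in six and one in four, larger than the criterion in section 1.
- A reader might also see a conflict between hospital admission (section 3.1) and emergency admission (sections 4.1 and 5.1). The former sits in a parenthesis that spells out emergency contacts, so this is wording only. Nor does the SAP say how a death enters the count, so a claim that early deaths would flatter a group has no basis in the text.

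None of this says which cause, which form or which model gives the primary result.

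**Conclusion.** The concern holds. Sections 3.1 and 5.1 disagree on cause, section 4.1 labels two forms as primary, and nothing in the SAP designates the decisive test or shares out the alpha. The error inflation is moderate: about 7-8% for number and time, and about 9-13% for four versions, resting on assumed correlations of 0.7 to 0.9 and on each version being tested at 5%. The stated power is correct for the any-cause binary contact, and reasonable for any-cause time to first event if hazards are proportional. It cannot be carried over to the count or to a falls-only outcome; the figures of about 47% and 31% for the latter rest on assumed risks of 30% and 20%, without deaths. The sample-size calculation itself is not at fault. An undetermined primary result should be settled before comparative data are seen.

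**What to change.** Before comparative data are seen:

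1. Use the same cause definition in sections 3.1, 4.1 and 5.1.
2. Name one cause, one form and one model as the primary test. It should be a version that the section 3.2 calculation supports, such as any-cause time to first contact or death, or the any-cause binary event within six months. Either would do; the first keeps an outcome that section 4.1 already labels primary.
3. State in section 3.2 whether death is part of the powered event.
4. Label the falls-specific, count, recurrent-event and single-component analyses as secondary. If the hierarchy was meant as a testing order, say so and give the order.
5. If more than one primary is kept, apply Holm or Hochberg and restate the power for each.

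The cost is SAP wording. The sponsor gives up claiming primary success on the other versions or, if several primaries are kept, accepts lower power for each: with a plain Bonferroni split, 73.2% for two tests and 64.1% for four, both at 50% v 45%.

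### The SAP names the stations attending a patient's later falls as a potential confounder, although that variable arises after allocation and exists only once a primary outcome event has occurred

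*SAP*

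**What the plan says.** SAP section 5.1 sets the basis of the comparison: "the primary analysis will be by 'treatment allocated". It then lists predictors such as distance to the emergency department at the index fall, age, gender and pattern of presentation, which "will be considered as covariates, and included in statistical modelling". The next sentence adds the item at issue, also to be allowed for: "potential confounders such as the sequence of base stations (and their trial allocation) from which paramedics attend patients who fall more than once". The paragraph closes by carrying its principles over to the quantitative secondary outcomes.

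The same section describes the primary outcome: "Primary outcomes comprise a hierarchy relating to further emergency healthcare contacts for falls, as measured by contacts with the 999 service", with emergency department contact, emergency admission and death as the other components. Section 3.1 gives it more broadly, "for any reason and for falls per recruited faller, and time to first contact or death". A 999 attendance at a later fall counts under either wording.

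Three other statements bear on the point. Covariates are screened: "those with an F value of less than 1 (that is, they increase the standard error of the estimate) will be excluded", and binary covariates with more than 90% of cases in one category are also dropped. A further analysis is planned: "Primary outcomes will also be jointly analysed using methods developed for recurrent event analysis". Section 6.3, on sensitivity analyses, does not mention the station sequence.

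**The concern.** A confounder of a randomised comparison would have to be related to allocation without being a consequence of it or of what follows it. Stations were randomised, so who attends a later fall is settled after the index allocation and cannot have influenced it. The variable also has a value within the follow-up window only if the patient has called 999 again for a fall. Everyone with a value has therefore had the event, and a patient without the event has none.

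If such a variable enters the logistic model or the Cox model for first event as a covariate, the treatment coefficient is no longer the effect of being attended by an intervention station at the index fall. The F rule gives no protection, because a variable that implies the outcome will normally have a large F and be kept. At stake is the primary estimate: a real effect could be attenuated or, under one coding, an effect could appear where there is none.

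**Working it through.** **The plan's own figures.** The quoted sentence carries no number; section 3.2 supplies the event rate and effect size used below. With pooled variance under the null, n per arm = [1.960·√(2·0.475·0.525) + 1.282·√(0.5·0.5 + 0.45·0.55)]² / 0.05² = 2094.2, so 2095 per arm and 4190 in total, as stated. The target is 25 × 0.998·4190/(25 − 0.002·4190) = 25 × 251.6 = 6290, as stated. For 4400 evaluable patients, 176 per station, the design effect is 1 + 175·0.002 = 1.35. The effective size is 4400/1.35 = 3259 and power is 81.6%, consistent with the stated 3260 and approximately 80%. These figures are not in dispute.

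**Assumptions not in the SAP.** Let s be the share of outcome events that are falls re-attended by a trial paramedic (30% or 60%). Let q be the share of those re-attendances that come from a station in the same arm as the index station (50%, 70% or 90%). Arms are equal in size, s and q are the same in both arms, and there is no clustering and no other covariate. Event risks are p₀ = 0.50 in control and p₁ = 0.50 (null) or 0.45 (design effect).

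**Method.** In a linear probability model, the adjusted difference is the average of the within-stratum risk differences. Each stratum is weighted by ab/(a+b), where a and b are the proportions of the intervention and control arms that fall in it.

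**Coding A: none/intervention/control.** In both re-attended strata every patient has the event, so the difference there is 0. In the stratum with no re-attendance it is p₁(1−s)/(1−s·p₁) − p₀(1−s)/(1−s·p₀), which is 0 under the null. For the design effect with s = 0.6 and q = 0.5:
- Stratum difference: 0.18/0.73 − 0.20/0.70 = −0.0391.
- Weights: 0.3573 for no re-attendance and 0.0711 for each of the other two strata.
- Adjusted difference: −0.0391 × 0.3573/0.4994 = −0.028.

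**Coding B: one indicator for a later intervention station, 0 otherwise.** Under the null with s = 0.6 and q = 0.9, the indicator is 1 for 0.5·0.6·0.9 = 0.27 of the intervention arm and 0.5·0.6·0.1 = 0.03 of the control arm.
- Difference among patients coded 0: 0.23/0.73 − 0.47/0.97 = −0.1695.
- Weights: 0.4165 for patients coded 0 and 0.0270 for patients coded 1.
- Adjusted difference: −0.1695 × 0.4165/0.4435 = −0.159.

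The same formulas give, in percentage points:

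| s | q | A, true effect −5.0 | B, no true effect | Patients with B = 1 (null) |
|---|---|---|---|---|
| 30% | 50% | −4.1 | 0 | 7.5% |
| 30% | 70% | −4.2 | −3.3 | 7.5% |
| 30% | 90% | −4.5 | −6.8 | 7.5% |
| 60% | 50% | −2.8 | 0 | 15% |
| 60% | 70% | −2.9 | −7.3 | 15% |
| 60% | 90% | −3.4 | −15.9 | 15% |

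A simulation of 400 trials of 4400 patients per scenario agrees to within 0.1 point. In it, coding A lowered power for the design effect from about 91-93% to 66-89%. Coding B rejected a true null in 62-100% of trials at q = 70-90%. Without the later-station variable, estimates were unbiased and null rejection was 3-7%.

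**The 90% rule.** Under the null, B = 1 in 0.5·s/2 = 0.25·s of patients. That is below 10% when s is below 40%, so the rule would drop the indicator in the 30% rows and keep it in the 60% rows. The rule does not apply to a single three-level factor.

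**Logistic scale**, the SAP's method for binary outcomes. Under B the indicator predicts the event perfectly, so those patients leave the treatment comparison. With q = 0.7 and no true effect, the odds ratio is (0.395/0.5)/(0.455/0.5) = 0.87 at s = 0.3 and (0.29/0.5)/(0.41/0.5) = 0.71 at s = 0.6. The design effect is (0.45/0.55)/(0.50/0.50) = 0.82. Under A the odds ratio is preserved if s is equal in the two arms, but the re-attended events no longer inform the comparison.

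**The case against.** The SAP does not say that any model adjusts for later stations. The predictors fixed at the index fall are explicitly assigned to the modelling; the station sequence gets looser wording, with no model, coding or outcome named. The section also plans recurrent-event analysis, where a sequence of attendances in patients with repeated falls is a natural object and past attendances can properly enter as history for later events. Cross-group attendance at later falls is a genuine contamination question. All of this stands. It shows that a sound use exists, but the SAP does not confine the variable to it: the sentence follows directly on the model covariates, in the paragraph on the primary outcomes, and calls the variable a confounder.

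A reader might infer that taking the sequence into account necessarily biases the treatment effect, or would produce a spurious benefit. The documents do not support that. Coding that separates no later attendance from attendance by either group, arguably closest to the SAP's wording, gives no bias under the null; nor does the single indicator when re-attendance is evenly split between arms. The 90% rule would remove the indicator in some plausible settings. The SAP gives neither the share of events re-attended by trial paramedics nor the same-arm share, so no single bias figure can be attributed to the plan.

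**Conclusion.** The defect is one of specification, and it stands. The SAP labels as a potential confounder a variable that is post-allocation and, within six months, observed only after a primary outcome event. It leaves open the variable's entry into the models that compare groups by allocation. Used in the binary or first-event model, it would condition on the outcome and contradict the section's own principle.

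The size is conditional. With a 50% event rate and 30-60% of events re-attended, full coding leaves the null intact but reduces a true -5.0 point effect to about -2.8 to -4.5 points on the linear scale. A single indicator that survives the 90% rule produces 0 at even same-arm re-attendance and about -3 to -16 points at 70-90%. Within that range, the values from 30% re-attendance (-3.3 and -6.8) are ones the rule would exclude. The re-attendance and same-arm shares are assumptions, and the calculations ignore clustering and other covariates. The conclusion that the variable does not belong in those models needs none of these figures.

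**What to change.** State in section 5.1 that the primary analysis compares patients by the allocation of the station attending the index fall, adjusting only for variables fixed at or before the index call. Remove the later-station sequence from the primary binary and first-event models, and stop describing it as a confounder. Make clear that the same restriction carries over to the secondary outcomes that follow these principles.

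If cross-group attendance at later falls is of interest, move it to section 6.3 as a prespecified sensitivity analysis labelled as a non-randomised comparison. One option is past attendances as a time-varying exposure in the recurrent-event model already planned, with the coding for patients with no later attendance stated.

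The cost is a change of SAP wording plus one optional sensitivity analysis.
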